**Half-way through radiotherapy schedules**

The only study measure to be completed will be hyperpolarized Xe-129 MR imaging involving up to a maximum of six xenon breath holds. Adverse events and serious adverse events will be reviewed.

**Final day of treatment and 3-months following completion of radiotherapy: -**

- AE/SAE review
- Arterial oxygen saturation
- Dyspnoea & CTCAE version 4 RILT assessment
- Hyperpolarized Xe-129 MR imaging involving up to a maximum of six xenon breath holds

**Two weeks after final xenon administration at 3-month post-radiotherapy**

- AE/SAE review via telephone consultation

**9.10. Discontinuation/Withdrawal of Participants from Trial Treatment**

Each participant has the right to withdraw from the trial at any time. In addition, the Investigator may discontinue a participant from the trial at any time if the Investigator considers it necessary for any reason including:

- Pregnancy
- Ineligibility (either arising during the trial or retrospectively having been overlooked at screening)
- Significant protocol deviation
- An adverse event which requires discontinuation of the trial medication or results in inability to continue to comply with trial procedures
- Disease progression which requires discontinuation of the trial medication or results in inability to continue to comply with trial procedures
- Withdrawal of Consent
- Loss to follow up

Withdrawal from the study will not result in exclusion of the data for that participant from analysis provided all baseline study measures have been completed.

The reason for withdrawal will be recorded in the CRF. If the participant is withdrawn due to an adverse event, the Investigator will arrange for follow-up visits or telephone calls until the adverse event has resolved or stabilised.

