**Ventilation/perfusion nuclear medicine scan (SPECT/CT)**

Ventilation/perfusion nuclear medicine scan will be completed at baseline only and is an optional study measure. This scan is performed using the 16-slice GE Discovery 670 scanner as per local protocol. The nuclear medicine scan involves three components: -

- Ventilation imaging – this involves the patient breathing in a gaseous tracer in aerosol form e.g. technetium-labeled diethylenetriamine pentaacetate (99mTc-DTPA) via a mouthpiece or mask.
- Perfusion imaging – this involves insertion of a cannula, and then an injection of a small volume, < 5 mL, of radioactive technetium labelled macro aggregates of albumin (99mTc-MAA). A gamma camera acquires images for both ventilation and perfusion components. Patients do not have to move to a different bed between the nuclear medicine and CT scans, so it is associated with minimum disruption.

Participants will be screened for contraindications to nuclear medicine scanning including known hypersensitivity to albumin or preference to avoid blood donation product. If a contraindication

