If the patient fails to breathe in sufficient xenon at the required time, the investigator may suggest that the procedure is repeated once or twice. One patient will not exceed six inhalations of xenon in a single day. In the unlikely occurrence of an adverse event, a radiographer will be able to access the participant immediately. Participants are monitored for at least 30 minutes after the final hyperpolarized xenon dose before they are discharged home. It is likely approximately 3 hours will have elapsed since administration of the first hyperpolarized xenon dose by this time. Participants will receive a telephone consultation 24 hours after completion of hyperpolarized Xe-129 MRI to review any AEs that have occurred in the interim following discharge. Furthermore, participants will attend hospital and see the Oncology clinical team on a daily basis during radiotherapy when they will have the opportunity to report any AEs relating to hyperpolarized Xe-129 gas. The study schedule includes follow-up by both the study team and Oncology clinical team in out-patient clinic at regular intervals throughout the 9 month trial duration. This will allow for review of possible AE/SAE two weeks after each hyperpolarized xenon scanning session.

Following the final xenon administration at the 3-month post-radiotherapy follow-up visit, participants will also receive a telephone consultation two weeks later to review AE/SAEs.

Hyperpolarized Xe-129 MR imaging will be performed using xenon hyperpolarized by a xenon hyperpolarizer (Polarean 9880) and imaged on a 1.5T MRI scanner. A dedicated Xe-129 chest coil will be used. Images will be obtained in the coronal plane. During each scanning session, up to four hyperpolarized Xe-129 MR sequences will be acquired with the participant undergoing four separate xenon breath holds. Hyperpolarized Xe-129 MR will be repeated at baseline to assess reproducibility. Total scanning time will be approximately half a day during each visit. The participant will spend a total of approximately 1 ½ hour within the MRI scanner during each visit. Image acquisition strategy will include:-

- Short echo proton MRI for co-registration purposes.

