**12.5. Procedure for Accounting for Missing, Unused, and Spurious Data.**

Efforts to measure all data as outlined in the trial protocol will be made. If a patient provides data from only one Xe-129 MRI scan, this will be included in analysis for mapping, but not for reproducibility. The data will be reviewed by [name], to confirm that it is robust, and any deviation from expected results will be reviewed to determine if this is due to scanning error, or other artefact.

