**12.6. Inclusion in Analysis**

All evaluable participants will be included in the analysis. Participants will be deemed not to be evaluable for reproducibility if either or both baseline Xe-129 MRI scans are not assessable.

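### Section 9.10 makes a withdrawn participant's data depend on every baseline test, including tests that the primary Xe-129 change endpoint does not need

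*Combined protocol and SAP*

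**What the plan says.** Section 9.10 has the only rule on what happens to the data of people who withdraw. Withdrawal is not to lead to "exclusion of the data for that participant from analysis provided all baseline study measures have been completed". Among its reasons for discontinuation are adverse events, disease progression, withdrawal of consent and loss to follow-up.

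Section 12.6 states: "All evaluable participants will be included in the analysis". The only evaluability criterion it gives is for repeat scans: "Participants will be deemed not to be evaluable for reproducibility if either or both baseline Xe-129 MRI scans are not assessable". Section 12.5 adds: "If a patient provides data from only one Xe-129 MRI scan, this will be included in analysis for mapping, but not for reproducibility".

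For lung-cancer patients, the baseline assessments in Section 9.5 are oxygen saturation, full pulmonary function tests, dyspnoea scores, RILT grading, V/Q SPECT/CT, thoracic CT, Xe-129 MRI and gadolinium MRI. The V/Q scan "will be completed at baseline only and is an optional study measure". For other diagnoses, Section 9.6 lists four items: oxygen saturation, dyspnoea, RILT and Xe-129 MRI.

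The primary endpoint in Section 6 is change in Xe-129 MRI from baseline to time points after radiotherapy starts.

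**The concern.** The condition in 9.10 bears no relation to what each endpoint needs. The primary endpoint needs a Xe-129 scan before radiotherapy and at least one after it starts. Lung function, CT, gadolinium MRI and V/Q imaging contribute nothing to that difference, yet a missing one can remove a withdrawn participant who has both scans.

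The condition also applies only to people who withdraw. Two participants with the same scans and the same missing test are treated differently because one of them left the study. Several of the listed reasons for leaving, adverse events and progression in particular, are plausibly tied to the lung damage that the imaging is meant to detect. The rule can therefore select the analysis set on something related to outcome. It is also stricter for lung-cancer patients, whose baseline list is longer.

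**Working it through.** **1. What the condition does.** 9.10 is worded as a promise to retain data, with a proviso. The proviso has no function unless an incomplete baseline leads to exclusion, so exclusion is the natural reading although it is never stated.

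**2. The rules side by side**, for a lung-cancer participant with assessable Xe-129 scans before and after radiotherapy starts and no gadolinium MRI at baseline:

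- Did not withdraw: 9.10 does not apply, and nothing in 12.5 or 12.6 removes the participant.
- Withdrew: 9.10 is not satisfied, so the participant is left out of the change analysis.

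For a withdrawn participant with a single baseline Xe-129 scan, 12.5 keeps the scan for mapping. Section 9.5 says: "Hyperpolarized Xe-129 MR will be repeated at baseline to assess reproducibility". If that repeat is a required baseline measure, 9.10 excludes what 12.5 includes. Whether it is required is not settled, because 7.1 and another paragraph of 9.5 say only that a sequence may be repeated.

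**3. Precision.** Section 12.2 gives a total of 30 without an effect size, SD, power or dropout rate, so there is no plan figure to reproduce. Assume a mean change with a t-interval, all 30 contributing before any exclusion, and results in units of the SD of change. The 95% half-width is t(0.975, n−1)/√n:

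- n = 30: 2.045/5.477 = 0.373 SD
- n = 27 (3 lost, assumed): 2.056/5.196 = 0.396 SD, about 6% wider
- n = 25 (5 lost, assumed): 2.064/5 = 0.413 SD, about 11% wider

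**4. How many might be lost.** Let w be the proportion who withdraw and m the proportion of those with an incomplete baseline. Both are assumed. Expected exclusions are 30·w·m, the chance of at least one is 1 − (1 − wm)^30, and the standard error grows by √(30/(30 − 30wm)).

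| w | m | Expected excluded | P(at least one) | SE factor |
|---|---|---|---|---|
| 10% | 10% | 0.3 | 0.26 | 1.005 |
| 20% | 30% | 1.8 | 0.84 | 1.03 |
| 40% | 50% | 6.0 | >0.99 | 1.12 |

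For the primary endpoint these counts are upper figures under each assumption, because an excluded participant must also have had usable scans before and after radiotherapy starts for a change score to be lost.

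**5. Bias.** If k of 30 are excluded and their mean change differs from that of the retained participants by d, the full mean is ((30 − k)·retained + k·excluded)/30. The retained mean is then off by (k/30)·d in absolute size: 0.10d for k = 3 and 0.17d for k = 5. The documents give no basis for d.

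**The case against.** The strongest reply is that few people can be caught. Someone must withdraw, lack a baseline test and still have Xe-129 scans on both sides of the start of radiotherapy. The baseline visit is compulsory (7.1). Only one follow-up visit is compulsory, so skipping the others is not withdrawal. Non-lung-cancer patients have four baseline items. CT is routine care (16.7) and goes ahead without contrast if contrast is contraindicated (9.5), and a contraindication to gadolinium is an exclusion criterion (8.3). Section 12.4 ends the study after follow-up of at least 30 patients is complete, which might mean that withdrawals are replaced, although 12.2 fixes the total at 30. All of this stands and limits the size of the problem. It does not rule out missing lung function tests or an uncompleted gadolinium scan, and replacing withdrawn participants would restore the number but not undo the selection.

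Three stronger readings are tempting, and the documents do not support them:

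- **Safety data are discarded.** The sentence concerns inclusion in analysis. Section 11 requires recording of adverse events, reporting of SAEs and cumulative SAE review whatever the state of the baseline, and 9.10 itself requires follow-up of events that lead to withdrawal. What is missing is a defined safety analysis set.
- **9.10 contradicts 12.6.** Evaluability is undefined beyond reproducibility, so 9.10 could be read as supplying part of the definition. This is an unreconciled ambiguity.
- **9.10 contradicts 12.5 on the primary endpoint.** The single-scan rule covers mapping only, and one scan gives no change score. The conflict is confined to the single-scan case in step 2 of the working.

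Whether the optional V/Q scan counts among the required measures is unclear. Treating it as required would strain the text, since a contraindication to it does not exclude the patient from the study.

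**Conclusion.** The point holds as a defect in the inclusion rule. On its natural reading, 9.10 removes usable Xe-129 change data from withdrawn participants because of tests that the primary endpoint does not need, and applies no such test to those who stay. Section 12.6 does not settle the matter, because it never says who is evaluable for change.

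The size is probably small. Losing 3 or 5 of 30 would widen the interval by about 6% or 11%, and those losses are assumptions. Possible outcome-related selection matters more. It is plausible from the listed reasons for withdrawal but cannot be quantified, because the documents give no rates of withdrawal or missing tests and no SD. The conclusion rests on reading the proviso as an exclusion; if that is not intended, the sentence still needs rewording.

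**What to change.** Delete the condition about baseline measures from 9.10 and replace it with a reference to analysis sets defined in 12.6, for example:

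- 9.10: *Data collected before withdrawal are kept and used in the analysis sets of Section 12.6, subject to the terms of any withdrawal of consent.*
- 12.6, primary change: *participants with an assessable baseline Xe-129 scan and at least one assessable Xe-129 scan after radiotherapy starts.*
- 12.6, other endpoints: *all participants with the measures that the endpoint needs.*
- 12.6, safety: *everyone who inhaled xenon.*

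The existing reproducibility and mapping rules can stay as two of the endpoint-specific definitions. Because 9.10 also lists ineligibility found retrospectively, the same paragraph should say how those participants are handled.

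The cost is about a paragraph of wording in a protocol amendment, with no new patients, visits or data. The downside is that denominators will differ by endpoint, so each result should be reported with its own n.

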**9.11. Definition of End of Trial**

The end of trial is the date of the last hospital visit of the last participant.

**Hyperpolarized Xenon gas MR Imaging in Radiotherapy****10. INVESTIGATIONAL MEDICINAL PRODUCT (IMP)****10.1. IMP Description**

No treatments are given as a part of the proposed study since the appropriate radiotherapy schedule is taking place as part of patients' routine clinical care.

Hyperpolarized Xe-129 lung MRI requires breathing in an investigational medical product, hyperpolarized xenon gas, Xe-129, which is described in detail below.

Xenon is an inert gas that is present in the atmosphere in low concentrations. It has no smell or taste. Breathing xenon or undergoing an MRI scan does not involve exposure to ionising radiation. We will administer a maximum of 6 x 1 Litre doses of hyperpolarized xenon gas to each participant per hospital visit for Xe-129 lung MR imaging. If it is not essential to give 100% xenon for imaging, the gas may be diluted with ultrapure nitrogen. The ratio of xenon to nitrogen will vary from 10% to 100% but the volume provided to the patient will always be 1 L.

The route of administration is inhalation. All female participants of child-bearing age will have had pregnancy excluded as part of their routine clinical care in Oncology prior to starting radiotherapy.

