**Hyperpolarized Xenon gas MR Imaging in Radiotherapy**

|  |  |  |
|--|--|--|
|  | 
imaging is a more reliable clinical indicator of patient respiratory tolerance to pulmonary radiotherapy than conventional lung function testing by determining the relationship between hyperpolarized Xe-129 MR imaging indices and functional patient outcome measures (dyspnoea and radiation-induced lung toxicity assessment).
 
To use functional lung information in virtual predictive and adaptive radiotherapy treatment planning.
  | 
dimensional CT (4D-CT) at baseline.
 
Retrospective comparison of modified radiotherapy treatment planning incorporating functional lung information from hyperpolarized Xe-129 MR imaging with conventional radiotherapy treatment plans.
 |
| Investigational Medicinal Product(s)       | Hyperpolarized xenon gas   |  |
| Formulation, Dose, Route of Administration | 
The xenon gas will be hyperpolarized in the Radiology department, Churchill Hospital.
 
We will administer a maximum of 6 x 1 Litre doses of hyperpolarized xenon gas to each participant per hospital visit for Xe-129 lung MR imaging. If it is not essential to give 100% xenon for imaging, the gas may be diluted with ultrapure nitrogen. The ratio of xenon to nitrogen will vary from 10% to 100% but the volume provided to the patient will always be 1 L.
 
The route of administration is inhalation.
 |  |

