**Hyperpolarized Xenon gas MR Imaging in Radiotherapy**

For the actual Xe-129 MRI scan, the patient breathes out, and then breathes in from a bag containing up to 1L of xenon, balance nitrogen. The total volume of gas participants inhale for Xe-129 MRI scans is 1L, however this may consist of a mixture of 50-100% hyperpolarized xenon and up to 50% nitrogen i.e. 500 mL to 1L of hyperpolarized xenon is mixed with medical grade nitrogen to make up a total volume of 1L. Breathing in xenon is challenging for some people because it has a density 4.55 time greater than air, which increases airways resistance (72). Therefore patients are sometimes given assistance with the respiratory manoeuvre by physically compressing the bag during inhalation. The patient receives a bag full of air or oxygen to practice this breathing manoeuvre before breathing xenon. Scanning then takes place during a breath hold for approximately 20 seconds, or during an inhalation-exhalation manoeuvre. This manoeuvre with scanning will be repeated up to four times to enable acquisition of all Xe-129 MRI sequences. The four inhalations may be different sequences or the same sequence may be repeated to assess reproducibility. There are currently three confirmed sequences (ventilation, ADC and dissolved phase) with further sequences under technical development that will be introduced during the course of the study period.

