**Safety considerations**

**Hyperpolarized Xenon gas MR Imaging in Radiotherapy**

At high concentrations xenon has anaesthetic properties. The minimum alveolar concentration (MAC) of xenon at sea level is 70% (77). Our patients will breathe a fraction of inhaled xenon (FiXe) considerably lower than this, and will inhale a single breath and therefore not approach the gas equilibrium that is required when defining MAC. Our patients will inhale 1L from residual volume, resulting in an approximate fraction of xenon (FXe) of 10-30%. The alveolar FXe would tend to be marginally lowered due to Xe in the anatomical deadspace of the large airways, and marginally raised due to Xe not entering non- or slowly communicating air spaces within the lungs. Thus the FXe that our patients will be exposed to is considerably below the dose required to induce anaesthesia, and well within safe limits. It is not possible for patients to breathe more than 1 L of xenon, since they are given a single bag of the gas. This procedure may be repeated up to four times during one imaging session. In the event that breathing and scanning are not entirely synchronised, one or two xenon breath holds may need to be repeated; so in total, each participant will undergo a maximum of 24 hyperpolarized Xe-129 breath holds during the four imaging visits over the 9-month study period.

A further safety consideration is patients' oxygenation, since they will be inhaling 1 L of anoxic gas, followed by a breath hold. However, participants will only be exposed to this low oxygen fraction for a single breath hold. The breath hold is approximately 30 seconds, although patients are free to take another breath sooner if they cannot manage this long. The amount of oxygen available in 3.5 L of 11% oxygen is 385 mL, which is considerably more than the oxygen requirement for the duration of the breath hold (assuming oxygen use is 250 mL/ min). These calculations assume all gas within the lungs is in communication with inhaled gas, which is often not the case in respiratory disease, however the safety margins are extremely large. Reassuringly, studies in chronic obstructive pulmonary disease (COPD) patients using this breathing technique observed a mean fall in oxygen saturations of only 1.2 % of baseline during observation at 2 minute intervals for 10 minutes (72). In the unlikely event that a patient desaturates by more than 10% immediately following Xe inhalation, this manoeuvre will not be repeated.

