**10.2. Production, Storage and Dispensing of IMP**

Xe-129 will be isolated from a gas mixture of 1.0% xenon, 10% nitrogen and 89% helium, manufactured in the USA and supplied by Spectra Gases Ltd, Littleport Cambridgeshire. It will be polarised via spin exchange optical pumping by laser, using the Polarean 9800 hyperpolarisation system. Xe-129 will then be frozen to isolate it from other gases and sublimated into Tedlar plastic bags for administration to participants via inhalation. The gas is labelled in accordance with EU trial directive requirements.

Each batch of Xe-129 will be tested using a Polarean 2881 polarization measurement system to ensure sufficient xenon gas is hyperpolarized to enable lung imaging. All staff involved in the process of Xe-129 manufacture will be trained to ensure that the manufacture is conducted safely to the correct technical specification. The manufacturing facility is licensed by the MHRA and each batch is manufactured to GMP standard and certified for release to the investigator by a Qualified Person according to the approved Standard Operating Procedures.

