***Calibration***

Calibration involves the patient breathing a small volume of xenon of approximately 100mL mixed with medical grade nitrogen for a total volume of 1L. The patient will be instructed to perform a standard breath hold for a short period of time (approximately 2 seconds). This is a set-up procedure for the scan enabling optimization of Xe-129 MR parameters according to patient height and weight as well as a practice run for the patient. The output from calibration (flip angle measurement) enables the best quality Xe-129 MR images to be acquired for each individual and is not be used to evaluate the study endpoints.

For calibration, hyperpolarization will take up to 10 minutes. The same manufacturing process as clearly described by SOPs to produce up to 1L of hyperpolarized Xe-129 will be adhered to. The only difference is the length of hyperpolarization time resulting in a much smaller volume (100mL) of hyperpolarized xenon gas being produced. Xe-129 will be isolated from other gases and

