**Hyperpolarized Xenon gas MR Imaging in Radiotherapy**

sublimated into Tedlar plastic bags in Radiology for administration to participants via inhalation in the MR suite. To make a total volume of 1L, medical grade nitrogen is added. These small calibration doses are not considered to be IMPs and do not require QP release.

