**10.3. Compliance with Trial Treatment**

Compliance auditing is not relevant to use of hyperpolarized xenon: a dose is only given by radiographers/ radiologists during the MR regional lung imaging itself. However, the volume of Xe-129 inhaled will be recorded on the CRF.

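### The synopsis and section 10.1 allow 10-100% xenon in the imaging bag where section 9.5 sets 50-100%, and no rule ties a participant's follow-up xenon volume to baseline

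*Combined protocol and SAP*

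**What the plan says.** Two ranges are given for the xenon content of a bag whose total volume is always 1 L.

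- Synopsis and section 10.1 (IMP Description): "If it is not essential to give 100% xenon for imaging, the gas may be diluted with ultrapure nitrogen", and then "The ratio of xenon to nitrogen will vary from 10% to 100% but the volume provided to the patient will always be 1 L".
- Section 9.5 (Hyperpolarized Xe-129 MR Imaging), on the actual scan: "this may consist of a mixture of 50-100% hyperpolarized xenon and up to 50% nitrogen". The same sentence restates this as 500 mL to 1 L of xenon.

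A bag of about 100 mL xenon in 1 L is described only for the calibration breath (sections 9.5 and 10.2). Section 10.2 says of these: "These small calibration doses are not considered to be IMPs and do not require QP release". Their output "is not be used to evaluate the study endpoints".

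On dose control and recording, section 10.2 says "Each batch of Xe-129 will be tested using a Polarean 2881 polarization measurement system", to confirm that enough of the gas is hyperpolarized for imaging. Section 10.3 says "the volume of Xe-129 inhaled will be recorded on the CRF". Sections 9.8 and 9.9 have follow-up measures done as in sections 9 and 12. The primary outcome (sections 6 and 12.1) is the change in Xe-129 MRI from baseline to later time points. Section 12 uses neither xenon volume nor polarization.

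**The concern.** There are two linked problems.

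First, the permitted dose of the investigational product differs between sections, by a factor of five at the lower limit (500 mL against 100 mL). A protocol should give one range.

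Second, the amount of xenon in the lung drives the MR signal, and the primary outcome subtracts one scan from another in the same person. If the follow-up bag holds less xenon than the baseline bag, the follow-up image has lower SNR for a reason unrelated to radiotherapy. The background in section 4.7 reads missing gas signal as ventilation defect, and lower ADC after radiation as possible fibrosis. On that reading, less xenon at follow-up would look like injury and more xenon would mask it. There is no unirradiated comparison of change over time: the other diagnostic groups in section 12.1 are compared on global ADC, not on change. So the design cannot separate a dose difference from a treatment effect.

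**Working it through.** **1. Which range fits the rest of the protocol?** The safety text in section 10.1 gives a breath of 1 L from residual volume "resulting in an approximate fraction of xenon (FXe) of 10-30" per cent, and uses a lung gas volume of 3.5 L in its oxygen calculation. That calculation reproduces: 3.5 L x 11% = 385 mL. Xenon fraction = xenon volume / 3.5 L:

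| Bag | Xenon | Lung fraction |
|---|---|---|
| 100% | 1000 mL | 1000/3500 = 28.6% |
| 50% | 500 mL | 500/3500 = 14.3% |
| 10% | 100 mL | 100/3500 = 2.9% |

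The 50-100% bags fall inside 10-30%. A 10% bag does not. The 10% limit cannot be explained as the calibration bag, because section 10.1 describes the IMP and its imaging doses, and section 10.2 places calibration doses outside the IMP.

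**2. Permitted dose difference between two scans of one participant.** Section 9.5: 1000/500 = 2-fold. Section 10.1 and the synopsis: 1000/100 = 10-fold. With matched volumes the ratio is 1.

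**3. What a 2-fold drop could do.** The documents give no SNR, defect threshold or diffusion weighting, so everything in this step is assumed:

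- median voxel SNR m = 20 with a 100% bag (range 10-40), proportional to xenon volume at equal polarization
- lognormal spread s = 0.5 (0.3-0.7)
- defect = voxel below t = 3 noise SDs (2-5)
- two-point ADC from Rician magnitudes, with b x ADC = 0.5 (0.25-1.5)

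False defect fraction = Phi(ln(t/m)/s).

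- Baseline, m = 20: Phi(ln(3/20)/0.5) = Phi(-3.79) = 0.007%
- Follow-up, m = 10: Phi(ln(3/10)/0.5) = Phi(-2.41) = 0.802%
- Difference: +0.79 points

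Measured ADC = ln(R(S0) / R(S0 exp(-b x ADC))) / b, where R is the Rician mean. It comes to 99.57% of the true value at SNR 20 and 98.28% at SNR 10, a difference of -1.3%.

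| 2-fold drop from SNR | Defect, central | Defect, range over s and t | ADC, central | ADC, range over b x ADC |
|---|---|---|---|---|
| 40 | +0.01 | 0 to +2.2 | -0.3% | -0.2 to -1.2% |
| 20 | +0.8 | 0 to +13.7 | -1.3% | -1.0 to -4.9% |
| 10 | +14.6 | +0.1 to +49.0 | -5.2% | -3.9 to -16.9% |

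**4. Is volume matching enough?** Take equal volumes, but polarization 20% above average at baseline and 20% below at follow-up: 1.2/0.8 = 1.5-fold signal. At SNR 10 and central settings this still gives +4.7 points and -2.2%. Polarization therefore needs to be known as well.

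**5. Would an 80-125% limit on volume x polarization control the bias?** A drop to 80% is 1.25-fold. At SNR 10 and central settings the residual is +1.7 points and -1.0%. Over the assumed ranges it reaches +9.1 points (s = 0.5, t = 5) and -3.7% (b x ADC = 1.5). The limit reduces the bias but does not bound it tightly.

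**The case against.** The best case for the plan runs as follows.

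- **Section 9.5 governs the scan.** Sections 9.8 and 9.9 send follow-up back to section 9, so the 10% figure has little practical force. This stands. A reader might infer that endpoint scans will differ 10-fold in dose. The documents do not support that: 9.5 sets 500 mL as the minimum for the scan, and the lung fraction in 10.1 agrees with it. The 10-fold case (+79 points and -39% at assumed SNR 20) should carry no weight.
- **Dilution is conditional.** It is allowed only where pure xenon is not needed, and nothing suggests that a sequence would be diluted at follow-up but not at baseline. Unsystematic variation would mainly add noise to a group mean. This stands, so systematic bias is possible but not shown.
- **The direction is inferred.** Section 4.7 is background on helium-3. Section 12 neither defines a defect by a noise threshold nor treats a lower xenon ADC as injury. This stands.
- **Safeguards exist.** Bag volume is fixed, flip angle is calibrated per patient, batches are tested, volume is recorded, readers are blinded to clinical data, section 12.5 reviews unexpected results, and section 12.7 allows further exploratory analyses. Procedures outside the documents may fix the volume. These help only in part. The batch test asks whether polarization is sufficient, not whether it equals baseline. A modest decline after radiotherapy need not look unexpected. An unseen procedure does not correct the protocol text.
- **Section 12 names no primary imaging parameter or test.** That is the larger gap, and it should be closed before any sensitivity analysis is specified.

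**Conclusion.** Both parts hold. The xenon range for imaging bags is inconsistent between sections, and 50-100% is the range that fits the rest of the protocol. Within that range the plan lets baseline and follow-up differ up to 2-fold in xenon dose, with no matching and no planned use of the recorded volume.

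The consequence is an avoidable source of noise and possible bias, not a threat that decides the result. Its size cannot be derived from the documents. Under the assumptions above it is about +0.8 defect points and -1.3% ADC for a halving at SNR 20. It becomes material only at low SNR, with a strict defect threshold or at high b x ADC. A reader might go further and infer that an apparent decline after radiotherapy would be a dose artefact. The documents do not support this, because they show neither a pattern of unequal dilution nor an analysis rule that would turn one into apparent injury.

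Severity is minor. The case for acting is that the change is specific and costs almost nothing.

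**What to change.** 1. In the synopsis and section 10.1, give 50-100% xenon for imaging bags and reserve 10% for calibration.
2. In section 9.5, require the participant's baseline xenon volume for the same sequence at the repeat baseline scan and at every follow-up. Where this is not possible, scan anyway and flag the pair.
3. Record the batch polarization already measured under section 10.2 on the CRF beside the inhaled volume.
4. In section 12, add a sensitivity analysis of the primary outcome that excludes flagged pairs, or pairs whose volume x polarization differs markedly from baseline. If 80-125% is used as the limit, call it a pragmatic choice and do not claim that it removes the bias.

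The cost is two wording corrections, one matching rule, one CRF field and one sentence in section 12, with no extra scans or measurements. The downside is less freedom to dilute at follow-up, and fewer pairs in the sensitivity analysis. Unmatched pairs stay in the primary analysis.
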